4.0 Subject Population

4.1 Inclusion Criteria

1. Patient currently has a Trifecta™ valve that was implanted at one of the U.S. or Canadian investigational sites during the Trifecta™ IDE study.
2. Patient met eligibility criteria prior to enrollment in the Trifecta™ IDE study.
3. Patient agrees to complete all required follow-up visits.
4. Patient provided written informed consent prior to any study related procedure, as approved by the governing Institutional Review Board (IRB) or the Ethics Committee (EC) of the investigational site.

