4.5 Method of Enrollment

Subjects are considered enrolled at the time the informed consent is signed.

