5.0 Confidentiality and Subject Informed Consent and Research Authorization

This study will be performed in accordance with applicable confidentiality, privacy and security, and data protection laws

The Investigator, or an individual designated by the Investigator, must obtain written study-specific informed consent and research authorization (using the most recent IRB/REB approved document) from an eligible subject prior to commencing any study-related procedures.

The process of obtaining informed consent must be consistent with the FDA published regulations, the Declaration of Helsinki and the reviewing IRB/EC. The subject or legal guardian must be given the opportunity to ask questions of, and receive satisfactory answers from, the investigator or study personnel prior to signing the consent document.

Subjects will be asked to provide consent so that data can be gathered. After the subject signs the informed consent document, the original is to be filed in the subject's medical record, a copy filed in the subject's study binder, and a copy given to the subject.

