6.0 Study Procedures

6.1 Summary of Study Procedures

Subjects will begin follow up visits according to the anniversary date of their Trifecta™ valve implant. However, prior to this visit, the patient must sign the informed consent.

Follow-up assessments will include the following (Refer to Table 7, Schedule of Assessments):

- Transthoracic-echocardiogram (TTE)
- NYHA functional classification assessment to be completed by a Study Investigator
- General clinical assessment
- Serious Adverse Event (SAE) Assessment

Table 7: Schedule of Assessments

	Screening	Year 2,4,6,8, and 9* (± 60 days)	Year 3,5,7 and 10* (± 60 days)	Early Termination
Informed Consent	X			
Echocardiogram			X	X
Clinical Assessment*			X	X
NYHA			X	X
Phone Assessment*		X		
Serious Adverse Events	X	X	X	X

*Subjects will continue the assessment schedule from the IDE study.

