Data summary and analysis will be performed based on all available data. Statistical analysis software SAS version 9.2 (or newer if available) will be used for the analysis, except when otherwise specified.

Valve Event Analysis

Survival (Kaplan-Meier) Analysis for time-associated mortality, valve-related mortality, SVD, and reoperation due to SVD will be based on the time to the first occurrence of the adverse event for each subject. Kaplan-Meier analysis will be performed to evaluate the freedom from adverse events data over time. Adverse events occurring in the postoperative period will be included in this analysis. The time to event will be determined from the date of implant to the first occurrence of the event (for subjects experiencing the event) or to the last date of contact (for subjects not experiencing the event).

Late Serious Adverse Event (Linearized) Rate will be reported for serious adverse events when appropriate, as defined by the number of late events per 100 late patient-years at risk:

$$\text{Linearized Rate (\%/late patient - year)} = \frac{\text{number of late events}}{\text{total late patient - years}} * 100\%$$

Late events are those that occur 31 or more days post-implant. The late patient-years for each subject are calculated from 31 days following implant to the last date of contact or adverse event as appropriate.

Data Presentation

Summary information will be provided in graphical and/or tabular format. For continuous variables, summary statistics (N, mean, standard deviation, and percentiles) will be provided. For categorical or ordinal variables, the number of subjects having each attribute and the percentage of total subjects used will be presented.

The following data will be presented when necessary:

1. Age at implant
2. Gender
3. Valve size
4. Medical history

The following analyses will be performed:

1. Survival (Kaplan-Meier) analyses for all primary and secondary end point events occurring in the post-operative period.
2. Number and linearized rates of subjects experiencing primary and secondary end point late events (>30 days post-implant).
3. A summary of specific hemodynamic (mean gradient, effective orifice area) data
4. NYHA functional classification assessment over time

Ad hoc analyses may be performed as appropriate.

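### The unbroken implant clock credits returning survivors with any unobserved interval, while deaths in it, and explants before first consent, have no stated route into the analysis

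*Combined protocol and SAP*

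**What the plan says.** Under Valve Event Analysis in Appendix A, Kaplan-Meier time is defined once for all endpoints: "The time to event will be determined from the date of implant to the first occurrence of the event", or to last contact for subjects without the event. The linearized rate uses the same kind of clock: "The late patient-years for each subject are calculated from 31 days following implant to the last date of contact", or to the event. Neither rule has an entry time or a provision for an interval without observation.

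Entry to the long-term study is conditional. Section 4.1 requires that "Patient currently has a Trifecta™ valve that was implanted" in the IDE study. Section 4.5 says "Subjects are considered enrolled at the time the informed consent is signed". Section 6.1 adds, about the first follow-up visit, "However, prior to this visit, the patient must sign the informed consent". Section 5.0 ties data gathering to that consent: "Subjects will be asked to provide consent so that data can be gathered".

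For subjects who never enrol, the Appendix A summary brings in their data from the IDE and the PAS, including those who died, were explanted, were lost or declined. Sections 4.4 and 7.2 end follow-up at loss. Section 7.4 nevertheless lets lost subjects re-enrol on a new consent, and gives no rule for the time between.

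**The concern.** By including deaths and explants recorded in the earlier studies, Appendix A avoids conditioning on survival to enrolment. The unbroken clock lets part of that conditioning back in wherever observation stops and restarts. A subject who dies in the interval cannot consent. The data held on that subject end with the earlier study, so the subject is censored there. A subject who survives the interval and consents is counted as at risk, event-free, throughout it. Time is therefore added for survivors without the matching events.

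The same holds for an explant before first consent, because section 4.1 requires the valve to be in place. At stake are the reported 10-year freedom estimates and the linearized rates, above all for all-cause mortality. The plan states no performance goal, so no formal decision depends on them.

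**Working it through.** The plan gives no event rate, gap length or consent rate, so there is no figure of its own to reproduce. The check measures the size of the effect on stated assumptions.

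**Inputs from the documents (Appendix A, Sample size):** about 650 active subjects and about 13 sites, 6 of them from the PAS. Horizon: 10 years from implant.

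**Assumptions:** constant mortality h of 5% per year (range 3% to 7%); non-PAS exit from the IDE spread evenly over years 1 to 4; PAS exit at year 5; PAS subject share equal to the site share, 6/13; 80% consent, unrelated to risk.

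**Formula.** Let O(t) be the subjects truly under observation at time t and R(t) those the plan counts as at risk. The expected estimate is S(10) = exp(−∫ h·O(t)/R(t) dt) over 0 to 10 years. With no gap, O = R and S(10) = exp(−0.5) = 60.65%, so the bias is zero. In a gap, R still contains the survivors who later consent, and O does not.

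**Hand check.** With gaps spread evenly over 0 to 1 year at non-PAS sites and full consent, the average time credited is about 0.5 × 7/13 = 0.27 year. Then 100 × [exp(−0.05 × 9.73) − exp(−0.5)] is about +0.8 point.

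**Numerical integration at 80% consent, overstatement of 10-year survival:**

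| Gap of 0 to 1 year | 3%/year | 5%/year | 7%/year |
|---|---|---|---|
| Non-PAS sites only | +0.51 | +0.69 | +0.79 |
| PAS sites only | +0.51 | +0.70 | +0.80 |
| Both | +1.02 | +1.40 | +1.60 |

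For the first row at 5%, the result is about +0.5 at 50% consent and +0.8 at 100%. The linearized death rate becomes 4.87 instead of 5.00 per 100 patient-years.

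**Primary endpoint.** With SVD reoperation at an assumed 0.5% per year alongside 5% mortality, true freedom is 95.1%. The non-PAS gap adds about 0.1 point. This is an upper bound, because every reoperation is treated as an explant.

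**Re-enrolment alone.** If half of surviving lost subjects return after 1 to 2 years, simulation gives about +0.1 point at 5% lost, +0.2 at 10% and +0.3 to +0.4 at 20%.

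**Events involved.** Non-PAS subjects: 650 × 7/13 = 350. The mean chance of death in the gap is 1 − (1 − exp(−0.05))/0.05 = 0.0246, so about 8.6 deaths. The same sum at 0.5% gives about 0.9 SVD reoperations.

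**Scale.** With an assumed 700 implants, the simulated standard error is about 2.0 points for 10-year survival and 1.0 for the primary endpoint. The non-PAS case is thus 0.7/2.0, about a third of a standard error.

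**The case against.** The strongest reply is that the main gap is not shown, and this stands. The footnote to "Table 7, Schedule of Assessments" says "Subjects will continue the assessment schedule from the IDE study", and Appendix A approaches subjects who were under active follow-up. Other text points towards a break. PAS sites and subjects are invited only when the PAS is complete, without saying whether that means each subject's year 5 or the whole study. Section 4.2 bars concurrent studies unless the sponsor approves. A continuing visit calendar also does not establish continuing surveillance between visits. The question stays open, and a reader who infers that a gap exists goes beyond the documents.

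Second, the one break the text permits, re-enrolment, has a small effect. This stands as well. Section 7.4 does not say that the valve-in-place criterion is rechecked, so an explant during loss may still be reported on return. Tracing before loss is declared may reveal some deaths. It would be wrong to say that all explants during loss are excluded.

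Third, Screening and phone questions about serious adverse events look back. They can recover an enrollee's non-fatal events, including SVD or a repair that leaves the valve in place. They do not reach anyone who died or never enrolled. The general statement that all available data are analysed gives no procedure for learning of those events.

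A reader might also infer a large bias. If every subject had a one-year gap at the same time, survival would be overstated by 100 × [exp(−0.45) − exp(−0.5)] = 3.1 points. Nothing in the documents supports that scenario.

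**Conclusion.** The point holds as a conditional one. Where observation breaks, the stated clock counts survivors' time without the deaths, or the pre-consent explants, that belong to it. If consent or return is unrelated to risk, the error favours the device, and a larger sample would not reduce it.

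On the assumptions above, 10-year survival is overstated by about 0.7 point (non-PAS gaps), 1.4 points (gaps at all sites) or 0.1 to 0.4 point (re-enrolment alone at 5% to 20% lost). The primary endpoint moves by about 0.1 point, and with no gap nothing changes. The constant rates, exit times, gap lengths and consent share are all assumed; the documents give none of them.

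The documents do not support a claim that the primary result is materially wrong, or that deaths recorded in the IDE or PAS are ignored. Severity is low to moderate: the reported estimates and linearized rates are affected, and no decision is. The narrower wording on prior data in section 4.3, compared with section 2.0 and Appendix A, is an editorial matter and adds nothing to this point.

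**What to change.** In Appendix A, define start-stop risk intervals for both Kaplan-Meier and late patient-years:

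- A subject is at risk from implant to the end of the period in which the IDE or PAS was still capturing that subject's deaths and reoperations, and again from consent or re-enrolment.
- The first interval must not end merely at the last visit. If surveillance in fact continued, counting deaths after that visit while cutting survivors' time understates 10-year survival by about 0.9 point for non-PAS sites, and 2.1 points if all sites are affected (simulation, same assumptions). Apply one window to events and to time, so that neither is counted without the other.
- Count gap time and gap events only where vital and valve status is ascertained for all subjects active at prior-study exit, or for all subjects declared lost. Where the IRB/EC permits, recording that status with dates at the planned approach is preferable.
- Report separately a first SVD or SVD reoperation that falls in an uncounted gap. That subject does not re-enter the risk set for that endpoint.
- Report the gap-length distribution and the numbers at risk by year.
- If all subjects share one common gap, give no Kaplan-Meier estimate across it without ascertained status. Nobody is then at risk in the gap, and start-stop entry repeats the overstatement: 100 × exp(−0.05 × 9) = 63.8% against 60.7% for one year.

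In the staggered scenarios above, start-stop entry brings the bias to zero. The cost is SAP wording and coding, a slight loss of person-time and slightly less favourable estimates. Status for non-consenters needs IRB/EC permission. Selective consent is not corrected: if half the subjects have 3% and half 7% yearly mortality and consent at 90% and 70%, survival is still overstated by about 0.9 point, and understated by about 0.9 with the consent rates reversed.

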Appendix B: Definitions

A. EDMUNDS CRITERIA AND SERIOUS ADVERSE EVENTS^{vii,viii ix,x}

Major Bleeding Event

Any episode of major internal or external bleeding that causes death, hospitalization, operation, pericardiocentesis, or permanent injury (e.g., vision loss) or requires transfusion. A bleeding event is reportable whether or not the subject is taking anticoagulation or antiplatelet drugs, since bleeding events can occur in subjects who are not receiving anticoagulants.

Embolic stroke complicated by bleeding is classified as a neurological event under “embolism” and is not included as a separate bleeding event.

Death

Valve-related Mortality: Death due to any of the following events involving the study valve: structural valvular deterioration, nonstructural dysfunction, valve thrombosis, embolism, bleeding event, endocarditis, or reoperation. Sudden, unexplained deaths of subjects with an operated valve are included as valve related mortality.

Sudden, unexpected, and unexplained deaths are sudden when they occur within one hour of an event of abrupt onset; unexpected if they occur in a previously well subject; and unexplained if no cause can be determined.

Other cardiac Mortality: Death resulting from cardiac causes, excluding valve-related mortality. Examples include congestive heart failure, acute myocardial infarction, and documented fatal arrhythmias.

Other cause Mortality: Death due to any cause, excluding valve-related mortality or other cardiac mortality.

Embolism

Embolism is any embolic event that occurs in the absence of infection after the immediate perioperative period (when anesthesia-induced unconsciousness is completely reversed). Only arterial emboli will be captured. Pulmonary emboli, cardiac mural thromboemboli and atherosclerotic particle emboli are not to be reported. Subsets of embolic events are:

Neurologic Event:

Any new, temporary, or permanent focal or global neurological deficit. Psychomotor deficits determined by specialized testing are not considered neurologic events related to operated valves. Types of neurologic events are:

- Transient Ischemic Attack (TIA): Fully reversible neurologic deficit that lasts less than or equal to 24 hours, and if an imaging study is performed, shows no evidence of infarction.
- Reversible Ischemic Neurologic Deficit (RIND): Fully reversible neurologic deficit that lasts more than 24 hours and less than or equal to three weeks.
- Stroke or permanent neurologic event: A neurologic deficit that lasts more than three weeks, causes death or lasts less than or equal to three weeks with a brain imaging study showing an infarction.

Systemic Embolic Event:

An operative, autopsy or clinically documented embolus that produced symptoms from complete or partial obstruction of a peripheral (non-cerebral) artery. Systemic events should be classified as:

- Minor: symptoms resolve completely without medical or surgical intervention
- Major: permanent injury or medical/surgical intervention required
- Fatal: death results as a consequence of the embolism or from related adverse events (less than or equal to 30 days or during the same course of hospitalization)

Endocarditis

Valvular endocarditis is any infection involving an operated valve. The diagnosis of operated valvular endocarditis is based on customary clinical criteria including an appropriate combination of positive blood cultures, clinical signs and/or histologic confirmation of endocarditis at reoperation or autopsy. Morbidity associated with active infection, such as valve thrombosis, thrombotic embolus, bleeding event, or paravalvular leak, is included under this category and is not included in other areas of morbidity.

Nonstructural Dysfunction

Nonstructural dysfunction is any abnormality resulting in stenosis or regurgitation at the operated valve that is not intrinsic to the valve itself. Nonstructural dysfunction refers to nonstructural problems that result in dysfunction of a study valve *exclusive of thrombosis or infection* diagnosed by reoperation, autopsy, or clinical investigation.

Examples of nonstructural dysfunction include: entrapment by pannus, tissue, or suture; paravalvular leak, inappropriate sizing or positioning, residual leak or obstruction from valve implantation or repair, and clinically significant hemolytic anemia.

Sudden or progressive dysfunction or deterioration of the study valve may be structural, nonstructural, or both as determined by reoperation, autopsy, or clinical investigation.

Reoperation

Reoperation is any operation that repairs, alters or replaces the study valve. The reasons for reoperation are to be reported and may include reasons other than valve-related morbidity, such as recall, excessive noise, or incidental or prophylactic removal.

Thrombolytic or catheter-aided therapy of valve-related morbidity is not considered reoperation; however, the morbid event that prompted the intervention should be reported.

Structural Deterioration

Structural valve deterioration is any change in function of a study valve resulting in an intrinsic abnormality of the valve that causes stenosis or regurgitation.

Structural valvular deterioration includes study valve dysfunction or deterioration *exclusive of infection or thrombosis* as determined by reoperation, autopsy, or clinical investigation. The term structural deterioration refers to changes intrinsic to the valve, such as wear, stent fracture, calcification, leaflet tear, stent creep, and suture line disruption of components (e.g., leaflets) of an operated valve.

Valve Thrombosis

Valve thrombosis is any thrombus, *in the absence of infection*, attached to or near the study valve that occludes part of the blood flow path or that interferes with function of the valve. Valve thrombosis may be documented by operation, autopsy, or clinical investigation. Valve thrombosis is categorized as follows:

- Obstructive valve thrombosis: The accumulation of thrombus on a replacement valve with (potentially) catastrophic hemodynamic or embolic consequences.
- Non-obstructive valve thrombosis: An incidental finding without (potentially) catastrophic hemodynamic consequences (e.g., thrombus on the outflow aspect of the bioprosthesis, etc.)

Serious Adverse Event

A serious adverse event is any adverse event on health or safety, that is fatal or life threatening, results in persistent or significant disability, requires intervention to prevent permanent impairment/damage, or an event that results in hospitalization or prolongation of hospitalization (> 24 hours).

B. OTHER STUDY RELATED DEFINITIONS**New York Heart Association (NYHA) Functional Classification:**

Class I: No limitations of physical activity. Ordinary physical activity does not cause undue fatigue, palpitation, or dyspnea.

Class II: Slight limitation of physical activity. They are comfortable at rest. Ordinary physical activity results in fatigue, palpitation, or dyspnea.

Class III: Marked limitation of physical activity. Comfortable at rest, but ordinary physical activity causes fatigue, palpitation, or dyspnea.

Class IV: Unable to carry out any physical activity without discomfort. Symptoms of cardiac insufficiency at rest. If any physical activity is undertaken, discomfort is increased.

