11.2 Secondary Endpoints

1. Freedom from all-cause mortality;
2. Freedom from valve related mortality;
3. Freedom from SVD.

Additionally, NYHA, specific hemodynamic parameters (e.g. for calculating mean gradient, EOA) and confounding factors, including but not limited to demographic data, anticoagulation/antiplatelet therapy, beta blocker and calcium channel blocker use, and coexisting medical conditions will be collected, to the extent possible, to aid and support the interpretation of the analysis.

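### NYHA Classes II and III share the same symptom criterion in Appendix B, so the II/III split in the NYHA-over-time summary rests on two unanchored adjectives

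*Combined protocol and SAP*

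**What the plan says.** Appendix B, under other study related definitions, gives four NYHA classes. In Class I, "Ordinary physical activity does not cause undue fatigue, palpitation, or dyspnea". The next two read "Class II: Slight limitation of physical activity. They are comfortable at rest. Ordinary physical activity results in fatigue, palpitation, or dyspnea" and "Class III: Marked limitation of physical activity. Comfortable at rest, but ordinary physical activity causes fatigue, palpitation, or dyspnea". The last begins "Class IV: Unable to carry out any physical activity without discomfort. Symptoms of cardiac insufficiency at rest".

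Section 6.1 lists the "NYHA functional classification assessment to be completed by a Study Investigator", and Table 7 schedules it at years 3, 5, 7 and 10 and at early termination. Section 11.3 and the Data Presentation part of Appendix A both list "NYHA functional classification assessment over time" as the fourth planned analysis. Section 11.2 gives NYHA a supporting role: it is among the data collected "to aid and support the interpretation of the analysis". It is not listed as a primary or secondary endpoint in section 3.2, section 11 or Appendix A.

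**The concern.** An ordered scale needs each step to differ from the next on something a rater can observe. Here the observable part of Class II, "Ordinary physical activity results in fatigue, palpitation, or dyspnea", reappears in Class III with only the verb changed. The rater is left to decide between slight and marked limitation with no stated activity level for either.

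At stake is how far the II/III split in the NYHA summary can be interpreted. Two investigators could place the same subject in different classes, and one investigator could do so at different visits, without either departing from the protocol. NYHA is the only functional scale named in the plan, and its purpose is to help readers interpret the valve results. The distinction could not be recovered later, because the documents describe collecting only the assigned class.

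**Working it through.** The plan gives no figure to reproduce on this point, and no sample-size or event arithmetic applies. The check is a comparison of the four definitions in Appendix B, followed by how the class is collected and used.

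**Step 1. The definitions side by side.**

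| Element | Class I | Class II | Class III | Class IV |
|---|---|---|---|---|
| Limitation | none | slight | marked | no activity without discomfort |
| At rest | not stated | comfortable | comfortable | symptoms present |
| Trigger | ordinary activity, no undue symptoms | ordinary activity | ordinary activity | any activity |
| Symptoms listed | fatigue, palpitation, dyspnea | fatigue, palpitation, dyspnea | fatigue, palpitation, dyspnea | cardiac insufficiency, discomfort |

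Classes II and III agree on three of the four elements (state at rest, trigger, symptoms) and differ only on the degree of limitation. Classes I and IV each have a symptom criterion of their own.

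**Step 2. Apply the definitions to two subjects.** Subject A is comfortable at rest and has symptoms only on ordinary activity. Subject B is comfortable at rest and already has symptoms on lighter activity, and so also on ordinary activity. Neither fits Class I, since both have symptoms on ordinary activity. Neither fits Class IV as written, since both are comfortable at rest. Both satisfy the rest, trigger and symptom clauses of Class II and also those of Class III. The scale therefore separates A from B only through the rater's view of slight against marked. The ordering of the scale suggests that B is the subject Class III was meant to capture, yet no class names that state.

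**Step 3. Look for a correction elsewhere.** Neither the protocol sections nor Appendix A contains another NYHA definition.

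**Step 4. Look for a downstream control.** Under section 7.0, only core laboratory echocardiographic measurements are analysed. Under Appendix A, the primary and secondary endpoints are summarised on Clinical Events Committee (CEC) adjudication. No equivalent is described for NYHA, which individual investigators assign at approximately 13 sites (Appendix A, Sample size).

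**Step 5. Trace where the class is used.** It feeds the summary over time. It does not enter the Kaplan-Meier analyses or the linearized rates, the criteria in sections 4.1 and 4.2 do not use it, and the Appendix B definitions of structural deterioration, reoperation and valve-related death do not refer to it.

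**Step 6. Size.** The net error in the Class III share at a visit is the share wrongly moved from II to III minus the share wrongly moved from III to II. The documents give neither term. They also give no NYHA distribution and no rate of rater disagreement, so no figure can be put on it.

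**The case against.** The strongest reply is that the classes are still distinct. Each definition opens with its own criterion, and no subject is both slightly and markedly limited. The class is assigned by an investigator, and section 11.4 says that investigators and staff are trained on the protocol and methods. NYHA carries no test, threshold or success criterion. Some disagreement between raters would occur under any wording, and disagreements in opposite directions partly cancel in a class share.

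Most of this stands, and it limits the point. A reader might infer that Classes II and III cannot be told apart at all, or that one subject satisfies both in full. The documents do not support that, because the degree of limitation still orders them. What survives is narrower: that degree has no activity anchor, and the parts of the definition that could provide one are the same in both classes. Training and investigator assessment may reduce inconsistency, but they do not supply the missing criterion.

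A reader might also infer a false time trend, since IDE and PAS data are pooled into the analysis datasets (section 2.0 and Appendix A). That would require the reading of the boundary to change across visits or studies. If the same wording and site habits persist, the error is roughly constant and trends are less affected. The earlier NYHA wording and the CRF are not in the documents, so a difference is something to check and cannot be asserted.

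**Conclusion.** The definition is defective as written, and the defect is minor. It leaves the II/III split in a descriptive, supportive summary open to inconsistent classification between investigators, sites or visits. It has no bearing on freedom from reoperation due to structural valve deterioration (SVD), freedom from SVD, all-cause mortality or valve-related mortality.

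The conclusion rests on two assumptions: that Appendix B is the definition investigators apply, and that the CRF does not already carry a clearer one. A reader might go further and claim that the resulting error could rival the true share of subjects in the higher classes. The documents give no input for such a comparison. It would also set gross rater disagreement against a net share, and it would not isolate the disagreement due to this line from the disagreement expected under any wording.

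**What to change.** - Correct the Class III line in Appendix B so that its trigger is activity below the ordinary level used for Class II.
- Use the corrected wording on the CRF at years 3, 5, 7 and 10 and at early termination.
- Compare it with the NYHA wording on the IDE and PAS forms whose data are pooled. If it differs, say so where NYHA over time is reported and show which visits were classified under which wording.

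The cost is one line of text and a form check, with no extra visits, data items or analyses.
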